When attributes of the tinnitus percept change following certain maneuvers or muscle contractions and somatosensory tinnitus is suspected, it suggests an interaction between the somatosensory and auditory systems (Levine, 1999; Shore et al, 2007; Ralli et al, 2017; Marks et al, 2018). Numerous studies have revealed that tinnitus can be somatically modulated in many people (see Ralli et al, 2017 for a review). Tinnitus modulations associated with the somatosensory system and somatic disorders are often attributed to cortical neuroplasticity initiated by subcortical changes occurring at the auditory brainstem level (Shore et al, 2007). The anatomical and physiological connections between the somatosensory and auditory pathways have been well documented (Dehmel et al, 2008; Shore et al, 2007; Shore et al, 2016; Wu et al, 2016) and are shown in Figure 1 (Cherian et al, 2013). The fact that somatic manipulations can directly influence the tinnitus perception for many patients (Shore, 2011) suggests somatosensory tinnitus is an indicator of an underlying musculoskeletal deficit of the head or neck which warrants taking a non-traditional approach to tinnitus management (Sanchez & Rocha, 2011). The Cleveland Clinic, an institution that is at the forefront of providing tinnitus rehabilitative services, has developed a protocol for assessing if tinnitus can be somatically modulated; when it can, the clinic provides these patients with individualized physiotherapy as part of the treatment regimen.

Research Design and Methods

General Summary of Procedures. To accomplish the goals of Aim 1 (address the prevalence of somatosensory tinnitus in Veterans with tinnitus), individuals who are enrolled for care at a VA facility or clinic will be contacted and screened over the phone. Based on the phone screening, a subset of Veterans will be invited to attend one in-person visit. To accomplish the goals of Aim 2 (develop a clinical framework to diagnose, assess, and treat Veterans with somatosensory tinnitus), a subset of Veterans identified with somatosensory tinnitus (knowledge gained at visit 1) will be given the option to attend 3 in-person individualized physiotherapy sessions from the

study physical therapist using an abbreviated therapy protocol modeled after protocols used at the Cleveland Clinic.

Subject Identification/Recruitment

We will use a variety of recruitment methods including any of the following:

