NCRAR Data Repository: Veteran subjects will be recruited from a pool of participants who previously participated in research projects at the NCRAR and gave their consent to be contacted for future studies. These authorized data can be found in the NCRAR data repository (MIRB#2874) and the audiology and rehabilitation research data repository (MIRB #3750). The NCRAR data repository and audiology and rehabilitation research data repository's SOP indicates that any investigator who has an approved IRB protocol and consent form can contribute and retrieve data from the repository.

Corporate Data Warehouse (CDW): Data in the CDW are generated, in part, from Veterans' electronic health records within the VA and include healthcare use, diagnoses, and prescription drug dispensation for those receiving VA care nationally. The CDW will be used to identify demographic information and diagnoses for health conditions of interest relevant to accomplish the aims of this research (e.g., audiologic test data, tinnitus). CDW data will be accessed and linked via the VA Informatics and Computing Infrastructure (VINCI) Data Application Request Tracker (DART). Once VA data are linked within the VINCI environment, they will be securely moved to a VA Portland Health Care System research server. [name] has worked on other projects that have successfully used this method for similar recruitment efforts.

Recruitment Letters: Veterans who are enrolled for care at a VA facility or clinic, and have tinnitus, will be mailed a recruitment letter informing them about the opportunity to participate in this research study.

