For participants who choose to be consented in-person, after the informed consent and HIPAA authorization forms are reviewed and signed, they will complete a screening evaluation to confirm eligibility for the study. For participants who consented via the IRB-approved Information Sheet, they will be reminded they provided consent over the phone and be asked if they want anything about the nature of the study to be reviewed with them prior to starting the screening procedures. The HIPAA authorization will then be reviewed and signed prior to any study procedures being conducted. In some cases, procedures will be repeated on later visits. Baseline testing includes tinnitus loudness-matching using an audiometer (optional) and a musculoskeletal screening exam. The following questionnaires will also be administered: Tinnitus Screener, Health History Questionnaire, Tinnitus History Questionnaire; Hospital Anxiety and Depression Scale; and the Tinnitus Functional Index, which is the primary outcome measure.

Data Analysis (Statistical Analysis Plan)

A Bayesian approach will be used to estimate the prevalence of somatosensory tinnitus in the VA population conditional on the phone screening data. The Bayesian prior probability distribution (i.e., “prior”) for this analysis is the meta-analysis based prediction derived from 4 published studies (Sanchez et al, 2002; Abel & Levine, 2004; Sanchez et al, 2007; Simmons et al, 2008). A sensitivity analysis will be conducted using a flat prior and a prior concentrated below 40% prevalence to evaluate the effects of the prior on the Bayesian posterior probability distribution.

We will evaluate the feasibility and tolerability of individualized physiotherapy performed in ~10 Veterans with somatosensory tinnitus. We will use the pilot data from questionnaires (e.g., TFI) and if available, 1 kHz loudness-matching results to document any reductions in tinnitus-related distress and perceived loudness following individualized physiotherapy. The change from baseline TFI score and 1 kHz loudness-match (in dB Sensation Level; dB SL) observed in this sample will provide the basis for sample size calculations in a subsequent large-scale Merit Review proposal.

Risks and Side Effects

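### Aim 1 labels its posterior a prevalence for the VA population, but it is estimated from volunteers reached by an unfixed mix of routes, and the only planned sensitivity analysis varies the prior

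*Combined protocol and SAP*

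**What the plan says.** The Data Analysis (Statistical Analysis Plan) section sets out the Aim 1 analysis: "A Bayesian approach will be used to estimate the prevalence of somatosensory tinnitus in the VA population conditional on the phone screening data". The main prior is a meta-analytic prediction from four published studies. One robustness check is planned: "A sensitivity analysis will be conducted using a flat prior and a prior concentrated below 40% prevalence". Its stated purpose is to show how far the posterior depends on the prior.

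The General Summary of Procedures words the aim as to "address the prevalence of somatosensory tinnitus in Veterans with tinnitus" and says that "individuals who are enrolled for care at a VA facility or clinic will be contacted and screened over the phone". The Aim 1 eligibility list asks only for Veteran status and chronic audible tinnitus; it does not mention VA enrolment.

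Under Subject Identification/Recruitment, the routes are open-ended: "We will use a variety of recruitment methods including any of the following". They are:

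- the research repository: "Veteran subjects will be recruited from a pool of participants who previously participated in research projects at the NCRAR";
- the Corporate Data Warehouse (CDW): "The CDW will be used to identify demographic information and diagnoses for health conditions of interest";
- letters: "Veterans who are enrolled for care at a VA facility or clinic, and have tinnitus, will be mailed a recruitment letter";
- outreach: advertisements, flyers, health care professionals, word of mouth and sign-up at events.

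The phone screen is then given to callers who have expressed interest. Those who fail it may be screened again at staff discretion.

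**The concern.** Prevalence is the whole of Aim 1, and the rationale section says it has not been studied in Veterans with tinnitus. The documents therefore offer no earlier Veteran figure against which to check the result.

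A population prevalence needs some link between the people measured and the population named. Here the link is not described. Nothing fixes how many people come from each route, and the routes differ in kind: some begin with the study contacting people on a list, others with the Veteran or a third party. People whose tinnitus changes with movement might be more or less ready to answer a call for a study of that subject, and this readiness might differ by route.

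The prior-sensitivity analysis is the only check beside the estimate. A reader of the results could take agreement across priors as support for the population claim, which it is not.

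**Working it through.** **No figure to reproduce.** The documents give no number to be screened, no source mix, no precision target and no prior parameters. All inputs below are assumptions. They show what the planned check can and cannot see; they do not measure bias.

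**1. What the pooled posterior depends on.** Assume one binomial proportion with a Beta(a, b) prior. With x positives among n screened, the posterior is Beta(a + x, b + n − x), with mean (a + x)/(a + b + n). Only the totals x and n enter. Recruitment source does not appear.

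**2. The planned check with x = 120, n = 200.**
- Flat prior, Beta(1, 1): 121/202 = 59.9%, 95% interval 53.1 to 66.5%.
- Assumed low prior, Beta(6, 14), with 84% of its mass below 40%: 126/220 = 57.3%.
- Assumed high prior, Beta(14, 6), standing in for an optimistic prior: 134/220 = 60.9%.

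**3. Three source patterns with the same total.** Split the 200 into sources of 80, 60 and 60. The by-source flat-prior mean is (x + 1)/(n + 2).

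| Pattern | Positives by source | Sum | By-source posterior means |
|---|---|---|---|
| A | 48/80, 36/60, 36/60 | 120/200 | 49/82 = 59.8%, 37/62 = 59.7%, 37/62 = 59.7% |
| B | 36/80, 39/60, 45/60 | 120/200 | 37/82 = 45.1%, 40/62 = 64.5%, 46/62 = 74.2% |
| C | 60/80, 33/60, 27/60 | 120/200 | 61/82 = 74.4%, 34/62 = 54.8%, 28/62 = 45.2% |

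All three patterns return the results of step 2 exactly. Reporting by source separates them.

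**4. Selection that acts on everyone.** Suppose the true prevalence is p and Veterans with somatosensory tinnitus are k times as likely to enter the sample. The expected sample prevalence is kp/(kp + 1 − p). At p = 60% it is 50% for k = 0.67, 69% for k = 1.5, 75% for k = 2 and 82% for k = 3. Take k = 2 and n = 200, so x = 150. Posterior means and 95% intervals are:
- flat Beta(1, 1): 151/202 = 74.8% (69 to 80%);
- Beta(7, 3), an assumed stand-in for the meta-analytic prior: 157/210 = 74.8% (69 to 80%);
- low Beta(3, 9), with 88% of its mass below 40%: 153/212 = 72.2% (66 to 78%).

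The three roughly agree and all miss 60%. Agreement across priors is therefore compatible with substantial selection. The value of k, and whether it lies above or below 1, cannot be learned from the documents.

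**5. Precision within sources.** Half-widths of the 95% flat-prior interval at 60% positive: 6.7 points for n = 200, 10.5 for n = 80, 12.1 for n = 60 and 16.6 for n = 30.

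**The case against.** The strongest reply has five parts.

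*This is a pilot, and its stated primary outcome measure is the TFI.* That stands as a limit on the stakes. The later sample size is to rest on change in TFI and loudness match, not on prevalence. It does not make the population label right.

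*The CDW covers people receiving VA care nationally and could supply a frame.* It could, and the lack of a probability sample is inferred from silence rather than stated. But a frame without a described draw or treatment of non-response does not give a population estimate, and the other routes are pooled with it.

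*The prior check does what it says, and would not always look reassuring.* Both are true. With the priors of step 2 and 18 positives among 30, the means are 19/32 = 59.4% (flat), 24/50 = 48.0% (low) and 32/50 = 64.0% (high), a 16-point spread. A reader might infer that the check would comfort the investigators whatever happened; that depends on the number screened, which is not given. What holds is narrower: the check does not respond to the recruitment mix.

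*By-source reporting does not remove selection.* Correct. Sources can agree while all are biased, or differ although the mix is representative. It describes the sample, which is why restating the target comes first.

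*The target wording is shorthand.* Largely so. A reader might take the SAP label to include VA users without tinnitus, but the aim statement and the Aim 1 criteria rule that out. The remaining question, whether VA enrolment is required, is a minor wording gap.

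**Conclusion.** The point holds in limited form. As written, Aim 1 would report a prevalence for the VA population from volunteers whose recruitment mix is not fixed, with no draw, non-response handling or analysis by source stated. The one planned sensitivity analysis concerns a different question and, under one pooled proportion, cannot show selection or differences between sources.

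A reader might go further and infer that the estimate will be biased, perhaps upward because people who notice modulation volunteer more readily. The documents do not support that: they give no number screened, no source mix and no response data, so direction and size are both unknown. The percentages in the working illustrate insensitivity under assumed inputs and nothing more.

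The consequence is confined to what Aim 1 may conclude. It should be corrected because the change is small and alters that conclusion. The absence of a rule on which screen counts after rescreening is a side issue with no shown effect.

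**What to change.** In the SAP:

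1. State the Aim 1 target as Veterans with chronic tinnitus who responded to recruitment and were phone-screened, in place of the VA population. Align the General Summary of Procedures, the Aim 1 eligibility list and the Data Analysis section on whether VA enrolment is required.
2. Record one recruitment source per person at first contact. Beside the prior-sensitivity analysis, report the posterior prevalence by source (CDW/letter, repository, outreach or self-referred) as a descriptive sensitivity analysis. For the letter and repository routes, also give the numbers contacted and screened. State that similar rates across sources do not rule out volunteer bias.

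As a minor safeguard, use one record per person where rescreening occurs, and say in advance which screen it comes from.

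The cost is SAP wording, one added data field and two sets of counts; recruitment, visits and treatment are unchanged. The downsides are a narrower stated conclusion and wide within-source intervals, about 10 to 17 points either side for assumed groups of 80 down to 30, so the by-source results should not be used for formal comparison.

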There are only minimal risks associated with these research procedures. The sound booth used for testing is extremely quiet, and some people find such quiet environments to be disconcerting/annoying. Subjects will be told they do not have to participate if this is a problem. All of the testing equipment is checked and calibrated according to a required schedule, so any risk of equipment malfunction is minimized. For all measurements, sound

levels are below those known to cause hearing damage. There is a small possibility, however, that certain sounds in the tests may seem loud to a subject and cause them temporary discomfort. In addition, some discomfort is occasionally associated with wearing earphones during audiologic and tinnitus testing. To minimize these risks, subjects will be told they can stop at any time and do not have to listen to any sounds they do not want to.

Minor anxiety and fatigue may be experienced when carrying out the testing and when completing questionnaires. People could react emotionally to some of the items on the questionnaires. These items ask about how people react to tinnitus and how it affects their life. To minimize this risk, individuals will be told they do not have to answer any questions they do not want to.

People with tinnitus have been known to report their tinnitus becoming louder following auditory testing. Usually these individuals report some discomfort during testing. Participants will be informed of this potential risk and told to report any discomfort during testing, which would result in testing being terminated immediately.

The musculoskeletal screening exam will be performed by a trained clinician. It is possible that the screening procedures could aggravate the subject's tinnitus, underlying dizziness, headache, ear discomfort, or neck symptoms. To minimize these risks, subjects will be told to let the clinician know immediately if symptoms appear or worsen in any way during the exam.

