For the individualized physiotherapy, Veterans will be working one-on-one with the physical therapist who will provide both exercises and manual treatments (i.e., physiotherapy) to correct any deficits that are identified using standard of care clinical procedures. After a treatment session, there is a minimal risk that the subject may experience an increase in tinnitus, discomfort associated with the cervical spine, jaw, or thoracic spine. To minimize subjects experiencing discomfort, they will be educated on: 1) proper form of the exercises and expectations; 2) how to prevent worsening of symptoms; and 3) what to do if symptoms worsen.

Participant Safeguards

This study does not include vulnerable populations. Additional safeguards have been established to minimize risk of noise exposure.

Suicidality

It is not expected that potential subjects will be suicidal. In the unlikely event that an individual expresses suicidal ideation during the screening phone call or if he/she indicates that he/she is suicidal at any time during the study, a "warm transfer" procedure will be implemented to connect the individual with a person at the Suicide Hotline. All research staff will be informed of the warm transfer procedure and phone number for the National Crisis [contact] (Veterans press "1" and non-Veterans stay on the line).

Language is included in the informed consent form that if participants express thoughts about wanting to harm themselves or others, the Principal Investigator or study team member may call the National Crisis Hotline at [name] (Veterans press “1” and non-Veterans stay on the line) or walk them to the Emergency Department as appropriate.

Benefits

Tinnitus is the most prevalent service-connected disability for Veterans and currently has no “cure.” Hearing loss is the second most prevalence service-connected disability for Veterans. Subjects may or may not personally benefit from participating in this study. However, by serving as a subject, they will contribute new information expected to benefit patients in the future. Data generated from this research will help to assess the effectiveness of a new therapeutic approach to reduce tinnitus distress and partially, or completely, suppress the tinnitus perception.

Subjects will benefit by learning about tinnitus. In some cases, people who are bothered by their tinnitus are helped simply by receiving information and having their questions answered.

Protected Health Information

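### Does the post-treatment Tinnitus Functional Index need a named visit or window before this pilot can use its change score?

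*Combined protocol and SAP*

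**What the plan says.** Screening/Baseline Tests lists the questionnaires for the first visit, among them "the Tinnitus Functional Index, which is the primary outcome measure". The same section says "Baseline testing includes tinnitus loudness-matching using an audiometer (optional) and a musculoskeletal screening exam". It gives no order for these items, and adds that some procedures will be done again at later visits, without saying which procedures or which visits.

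Data Analysis (Statistical Analysis Plan) sets out to assess feasibility and tolerability in about 10 Veterans. It will also document any reduction in distress and "perceived loudness following individualized physiotherapy", using the loudness match only where it is available. "The change from baseline TFI score and 1 kHz loudness-match" are then to inform the sample size of a later proposal.

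General Summary of Procedures describes one in-person visit and, for a subset, three physiotherapy sessions; Aim 2: Exclusion Criteria shows that these are weekly. Subject Compensation gives 30 dollars per visit and 120 dollars for a treated Veteran who attends everything. Protected Health Information refers to follow-up visits once, when explaining why contact details are kept, and defines none.

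Risks and Side Effects carries three relevant cautions: "After a treatment session, there is a minimal risk that the subject may experience an increase in tinnitus"; "People with tinnitus have been known to report their tinnitus becoming louder following auditory testing"; and, for the musculoskeletal exam, "It is possible that the screening procedures could aggravate the" subject's tinnitus or other symptoms. On questionnaires it says "individuals will be told they do not have to answer any questions they do not want to".

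**The concern.** A change score has two ends, and only the baseline end is placed. On the written schedule, an in-person TFI at the last visit is taken either before session 3, when it reflects two of the three sessions, or after session 3 on the same day, when the protocol's own risk text allows for more tinnitus. At the first visit the TFI might be given after an exam or a loudness match that could aggravate symptoms. A raised baseline would overstate improvement, and a raised final score would understate it. If placement varied between Veterans, the SD of the change would also grow. There is no rule for the TFI of those who stop sessions early, or for skipped items. Because the change is to feed the sample size of the next trial, any distortion would carry forward.

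**Working it through.** **1. Visit count.** Inputs from Subject Compensation and General Summary of Procedures: 120 / 30 = 4 visits; 1 screening visit + 3 sessions = 4. The stated total is reproduced. A fifth paid visit would give 5 × 30 = 150 dollars, which does not match. So no paid in-person visit follows session 3. With weekly sessions, session 3 falls 7 × (3 − 1) = 14 days after session 1. A mailed or telephoned TFI would leave the total unchanged; it is neither described nor excluded.

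**2. Do the documents show a bias?** Set the texts side by side.
- The post-session risk is called minimal, with no size or duration.
- The caution about auditory testing adds that those affected usually report discomfort during the test, and that testing stops at once if discomfort is reported.
- The questionnaire items are described as asking how people react to tinnitus and how it affects their life. That is not a reading of loudness at that moment.
- The Benefits section says the approach is meant to reduce distress and to suppress the percept partly or wholly. Temporary same-day relief is therefore as open as temporary aggravation.

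Neither the size nor the direction of any effect on the TFI can be derived.

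**3. How much would an assumed shift matter?** The documents give no SD or effect size, so everything here is in SD units of the change, with 10 paired scores assumed.
- Half-width of the 95% confidence interval for the mean change: t(0.975, 9 df)/√10 = 2.262/3.162 = 0.72 SD.
- An assumed placement shift of 0.1 SD: 0.1/0.72 = 0.14, about one-seventh of that half-width.
- Root mean squared error of the mean change: √(1/10) = 0.316 with no shift; √(0.1 + 0.01) = 0.332 with a shift of 0.1 SD (+5%); √(0.1 + 0.04) = 0.374 with 0.2 SD (+18%).
- Mixed placement, with half the Veterans assumed to be shifted by 0.2 SD: added variance 0.25 × 0.2² = 0.01, so the SD is multiplied by √1.01 = 1.005. The 95% confidence interval for the SD from 10 pairs already runs from 0.69 to 1.83 times the observed value.

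**4. Sample-size sensitivity.** Assume a later two-arm trial, two-sided 5%, 80% power and a t-test. A standardised change of 0.5 needs 64 per arm, 0.4 needs 100 (100/64 = 1.56) and 0.6 needs 45 (45/64 = 0.70). These swings look large, but they show how steep any sample-size formula is. For an observed change of 0.5 SD, the pilot's own interval is 0.5 ± 0.72, or −0.22 to 1.22. It includes no change at all, so pilot size dominates.

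**5. Cost of a separate visit.** About 10 × 30 = 300 dollars in vouchers, before staff time, plus amended compensation and consent text and one more in-person contact for a study that is trying to limit them.

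**The case for a change.** The strongest case for a change is that this is the named primary outcome, and that supplying its change is the sample's stated use, so calling the study a pilot is no answer. A fixed time point needs no proof of bias to be worthwhile: without one, a later planner may not know whether the change reflects two sessions or three, or the same day or a later one. Giving the TFI first at each visit would cost nothing.

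Much of this stands as good practice. The text does not settle the time point, and the sentence about repeating procedures does not supply it. But for a change that is to follow physiotherapy, the natural reading is a score at or after the last session, and with about 10 participants the study team can apply one time point and report it with the result. The remaining items (order at the first visit, early stoppers, skipped questions) are also unstated details, and none is shown to alter a result. An extra visit a fixed number of days after session 3 is only one reasonable choice among several, and nothing in the documents makes it better than a score on the day of the last session.

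**Conclusion.** No change to the plan is needed. The omission is confirmed: there is no stated time for the post-treatment TFI, and 120/30 = 4 visits leaves none after session 3. It is missing detail that the study team can fill sensibly. It is not shown to make the change score wrong.

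The main stated purpose in the treated group is feasibility and tolerability, and the SAP sets out no efficacy test that depends on the TFI. For the planning use, an assumed shift of 0.1 SD would raise the error of the mean change by about 5%, against a 95% half-width of 0.72 SD that comes from having about 10 pairs.

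This conclusion rests on two assumptions: that the score is collected at or after the last session, and that any placement effect is small relative to the SD of the change. The documents neither support nor exclude a larger effect.

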Research Protocol

Title

A new therapeutic approach for somatosensory tinnitus

Investigators

PI: [name]

Specific Aims/Purpose

The purpose of this study is to address the immediate clinical need to improve the way the VA screens and evaluates tinnitus patients by piloting an approach modeled after what is done at the Cleveland Clinic. Results of this study will provide pilot data to be used in a large-scale Merit Review proposal. Long-term objectives are to adapt Cleveland Clinic's interdisciplinary approach to diagnose and treat somatosensory tinnitus for use in a new population: Veterans with tinnitus.

Scientific Rationale and Significance

Somatosensory tinnitus is suspected when the perceptual characteristics of tinnitus (e.g., pitch, loudness, timbre) are altered following certain head or neck maneuvers, forceful muscle contractions, or eye or jaw movements. Prevalence estimates range from 60 to 80% of tinnitus patients being able to somatically modulate their tinnitus in some manner (Ralli et al, 2017). The Cleveland Clinic, an institution at the forefront of tinnitus care in the United States, has developed a protocol for assessing if tinnitus can be somatically modulated and, when it can, implementing an established treatment regimen that has been successful in a majority of these patients. The prevalence and treatment of somatosensory tinnitus has not been studied in Veterans who suffer from tinnitus. The proposed research is the first step in achieving our long-term goal to develop a clinical framework for diagnosing, assessing, and treating somatosensory tinnitus in Veterans.

Of the millions of Veterans with tinnitus, many suffer negative consequences such as anxiety, insomnia, and concentration difficulties (Liu et al, 2015). Because the underlying mechanisms are still unclear, classification methods rely on categorizing tinnitus according to its characteristics. Many cases of somatosensory tinnitus involve concomitant pain or stiffness in the musculature of the head and neck. Other clinical features include tinnitus onset following head or neck trauma. Tinnitus and musculoskeletal disabilities of the head and neck are highly prevalent in Veterans (Veterans Benefits Administration, 2016); therefore, it is logical to postulate that a significant percentage of these Veterans have the clinical features suggestive of somatosensory tinnitus.

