Current clinical practice at the VA Portland Health Care System (VAPORHCS) is for Veterans who report tinnitus to be seen in the audiology clinic to assess their hearing ability and communication needs. VA clinicians do not routinely perform an in-depth tinnitus assessment and no standard guidelines exist recommending questions or screening procedures to identify tinnitus fluctuations or triggers. Going one step further

and evaluating the influence of somatic factors on the Veteran's tinnitus perception is rarely done. Veterans whose tinnitus is influenced by somatic movements suggests the possibility of an underlying head or neck musculoskeletal deficit that is being overlooked, which if treated, would help the Veteran patient to regain normal functioning.

In general, there is a lack of understanding as to why some tinnitus patients report benefit from one treatment over another. One possible explanation is that some types of tinnitus are more responsive to select treatments. Therefore, a critical need exists to develop methodological and clinical tools capable of assessing and subtyping tinnitus so that controlled studies can be done to address this gap in our knowledge. In the absence of this knowledge, patient factors are often examined to determine the likelihood of successful treatment outcomes (Theodoroff et al, 2014). By examining patient factors of individuals who respond favorably to an intervention, including what "type" of tinnitus they have, insight is gained as to what aspects of the patient and types of tinnitus are best suited for particular treatments. The focus of this proposal is a specific tinnitus subtype known as somatosensory tinnitus.

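### Does the SAP need to say which pilot quantity, and with what allowance for imprecision, will size the later Merit Review study?

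*Combined protocol and SAP*

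**What the plan says.** Under Specific Aims/Purpose the protocol states: "Results of this study will provide pilot data to be used in a large-scale Merit Review proposal". Under Research Design and Methods, a subset of Veterans identified with somatosensory tinnitus "will be given the option to attend 3 in-person individualized physiotherapy sessions"; no comparison group is described. The Data Analysis section plans to assess feasibility and tolerability of "individualized physiotherapy performed in ~10 Veterans with somatosensory tinnitus". It will use questionnaires such as the TFI "and if available, 1 kHz loudness-matching results to document any reductions in tinnitus-related distress and perceived loudness". The changes in these two measures "observed in this sample will provide the basis for sample size calculations in a subsequent large-scale Merit Review proposal".

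The Screening/Baseline Tests section makes loudness matching optional and lists "the Tinnitus Functional Index, which is the primary outcome measure". No section names the summary statistic to be carried forward, an interval for it, or a target difference for the next study. The design of that study is not described either. The nearest remark is in Scientific Rationale and Significance, where tools for subtyping tinnitus are wanted "so that controlled studies can be done to address this gap in our knowledge".

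**The concern.** Supplying data for a larger proposal is a stated purpose of this study, and the sizing sentence is the main use given for the change scores beyond documenting any reduction. Two quite different uses fit the words.

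- **The SD of the change as a planning value.** This is a normal use of a pilot, but with about 10 people the SD is poorly determined.
- **The mean change as the target difference.** This is weaker. The mean is also imprecise, and without a comparator it may contain improvement that a control group would share.

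Loudness match is optional, so its n could be below 10. A careless use of either quantity could leave the next study too small or needlessly large. Naming the quantity in advance would also remove the freedom to pick whichever input gives a convenient sample size.

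**Working it through.** There is no sample-size figure in the documents to reproduce. They give about 10 Veterans, and no alpha, power, SD or target difference. The calculations below therefore assume a two-sided 5% test, 80% planned power, normally distributed changes and n = 10 exactly.

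**1. Imprecision of the SD.** With 9 degrees of freedom the 2.5% and 97.5% chi-square points are 2.700 and 19.023. The 95% limits for the SD, as multiples of the estimate s, are

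- lower: √(9/19.023) = 0.688
- upper: √(9/2.700) = 1.826

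For a fixed target difference the required N is proportional to the variance, so it runs from 0.688² = 0.47 to 1.826² = 3.33 times the point figure. That is about a 7-fold range.

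**2. Consequence for power if only the SD is used.** Let σ be the true SD, assumed the same in the next study. By normal approximation, with 1.960 + 0.842 = 2.802,

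true power = Φ(2.802 × s/σ − 1.960).

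- Power is below 65% when s/σ < (1.960 + 0.385)/2.802 = 0.837. The probability is P(χ² with 9 df < 9 × 0.837²) = 0.291.
- The median of s/σ is √(8.343/9) = 0.963, which gives median power Φ(2.802 × 0.963 − 1.960) = 0.77.

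So the typical loss is about 3 points against the planned 80%, with a sizeable lower tail.

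**3. Dependence on the equal-SD assumption.** If the next study's SD were 0.8 or 1.2 times σ (assumed values), the cut-off 0.837 becomes 0.670 or 1.005. The share of pilots leading to power below 65% becomes about 9% or 57%. The 29% is therefore an illustration under one assumption and does not hold for every possible next study.

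**4. Smaller n for loudness match.** If only 8 or 5 people had it (assumed), the SD limits become 0.66 to 2.03 or 0.60 to 2.87 times the estimate. The share below 65% becomes 33% or 41%.

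**5. If the mean were the target.** Its 95% half-width is t(0.975; 9)/√10 = 0.715 SD. Any power figure for this use must include the sampling error of both mean and SD. Suppose the true change is 0.5 SD, none of it is non-specific, and the study is sized only when the observed mean is positive (all assumed). Simulation then gives a median power of about 74%, and 43% of pilots fall below 65%. If 25% of the change is non-specific and the next study is controlled (assumed; the documents give no figure), the median is about 50%, with a 10th to 90th percentile range from about 17% to nearly 100%.

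**6. Where the decision is made.** Steps 1 to 5 describe how a later sample size could go wrong. That calculation belongs to the Merit Review proposal. The Protected Health Information section says all test results and questionnaire responses are banked, and that agreeing to this is a condition of taking part. Every input above (n, mean, SD and intervals, for TFI and for loudness match where measured) can therefore be obtained when the proposal is written.

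**The case for a change.** The strongest case for a change is that it costs a few sentences and no visit, measurement or participant. The wording can be read as making the observed mean the target, which is the riskier use. Committing before the data are seen also protects against a convenient choice later.

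Part of this stands. The text is silent on the quantity and its uncertainty, and a line on both would make the intention clearer. But silence is the whole of the defect. Saying that the data provide a basis for sizing does not commit the sponsor to the mean, or to a point SD taken without allowance; it is compatible with showing N across the interval for the SD. The safeguard against a convenient choice lies mainly in the later proposal, which has to justify its own target difference and variance. Fixing the target or the main sizing endpoint here would settle features of a study whose design these documents do not describe. The documentary hints about non-specific change and controlled studies are general remarks and say nothing about that design.

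**Conclusion.** No change is needed. This is missing detail in a forward reference to another study, of a kind that whoever writes the later proposal can be expected to fill. The imprecision is large: a 7-fold range in required N at n = 10. About 29% of pilots would lead to true power below 65% if the raw SD were used with a fixed target and the same SD held in the next study. Those figures rest on assumed alpha, power and normality, and the 29% also rests on equal SDs. They bear on how the Merit Review study should be sized. This study's prevalence estimate, its feasibility and tolerability assessment and its description of TFI change are the same whether or not the sentence is expanded, and the data for a sound later calculation will be on hand.
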